### Matching procedure

#### *1:1 matching*

Each patient from Graz (i.e., undergoing posaconazole prophylaxis) was matched as a case with one control from Genoa and one control from Rennes (i.e., not undergoing posaconazole prophylaxis), employing two separate 1:1 propensity score (PS) matching procedures (one for identifying the control from Genoa and one for identifying the control from Rennes) [2,3]. The following variables were considered for matching cases with controls: (i) age; (ii) sex; (iii) treatment with tocilizumab; (iv) time at risk. We did not match for systemic steroid treatment since all patients from Graz received systemic steroids, thus we consider for possible match only those controls receiving systemic steroids in Genoa and Rennes (i.e., the majority of patients in the two centers). Time at risk was defined as follows: (i) for cases: days on posaconazole prophylaxis plus, if present, days in intensive care unit before posaconazole prophylaxis initiation; (ii) for controls: days in intensive care unit. In order to guarantee equal time at risk in cases and respective controls, we started by matching the case with the longest time at risk (53 days) to possible controls with time at risk equal or longer than 53 days. Then, we selected the case with the second longest time at risk and possible remaining controls with equal or longer time at risk. The procedure was repeated until all cases were matched to one control from Genoa and one control from Rennes. Eventually, for the study analyses, we considered only the period of time at risk in controls (starting from intensive care unit admission) that was equal to the time at risk in the respective case (in order to have an exactly equal time at risk in cases and their respective controls).

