#### *1:1:1 matching (for sensitivity analysis)*

The 1:1 PS matching described above is based on minimizing the distance between a case and a control. Therefore, for a given case from Graz, the two 1:1 PS matching procedures separately selected a control from Rennes and a control from Genoa. However,

this triplet of individuals may be not the one that minimizes the area or perimeter of the triangle formed by the three subjects [4]. Therefore, as sensitivity analysis, we conducted a logistic regression on all patients with observation time greater than or equal to the longest time at risk for the cases (thus, one case and all potential controls with equal or longer time at risk) to find for each subject the probability of belonging to the center of Graz (p1), the probability of belonging to the centre of Rennes (p2) and the probability of belonging to the centre of Genoa (p3). These probabilities sum up to 1, so we considered only the first two probabilities to figure each subject in a cartesian plane with x-axis p1 and y-axis p2. Then, we calculated the perimeter of the triangle resulting from each combination of the case with two controls (one from Genoa and one from Rennes) and chose the pair of controls for which that perimeter was the smallest. Subsequently, we repeated the procedure for the case with the second longest time at risk and all remaining potential controls with equal or longer time at risk. The procedure was then repeated until all cases were matched to one control from Genoa and one control from Rennes (1:1:1 matching)

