#### Assessment of impact of posaconazole prophylaxis on the risk of CAPA after matching

After 1:1 matching, the risk of CAPA was compared between Graz and the other centers by means of multivariable logistic regression. Besides center, other variables included in the multivariable logistic regression model were: (i) European Organization for Research and Treatment of Cancer/Mycoses Study Group Education and Research Consortium (EORTC/MSGERC) risk factor present at ICU admission; (ii) presence of extracorporeal membrane oxygenation (ECMO). A sensitivity analysis including the same variables was also conducted after 1:1:1 matching.

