#### Secondary analyses

To assess the prognostic impact of CAPA, 90-day survival in patients with and without CAPA after 1:1 matching was presented graphically using Kaplan-Meier curves, and compared with the log-rank test. To partly avoid immortal time bias, Kaplan-Meier curves were built as landmark analyses with different time of origin (15, 30, and 45 days after ICU admission) including patients still on follow-up at the selected time of origin, and excluding patients developing CAPA after the selected time of origin. It should be acknowledged that residual immortal time bias was present in patients from Genoa and Rennes in this secondary analysis, owing to their matching for time at risk (for the development of CAPA) in the primary study analysis (i.e., patients from Genoa and Rennes always remained alive for at least the time at risk of their respective case from Graz in the primary analysis). A sensitivity survival analysis was also conducted after 1:1:1 matching.

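### Matched controls are selected on their later ICU stay, so the CAPA odds ratios can be biased either way if CAPA changes stay, and the one analysis without this rule has inconsistent denominators

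*SAP*

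**What the plan says.** In this SAP a case is a Graz patient on posaconazole, not a patient with CAPA.

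- **Eligibility (1:1 matching).** The longest case is matched "to possible controls with time at risk equal or longer than 53 days", and the same condition is applied to each later case. For controls, time at risk is days in ICU, with no stop at CAPA. For cases it is "i) for cases: days on posaconazole prophylaxis plus, if present, days in intensive care unit before posaconazole prophylaxis initiation".
- **Matching variables.** The list is "i) age; (ii) sex; (iii) treatment with tocilizumab; (iv) time at risk". The text does not say whether time at risk entered the propensity score or acted only through eligibility.
- **Truncation.** After selection, the control's period is cut to the case's length, "in order to have an exactly equal time at risk in cases and their respective controls".
- **Sensitivity analysis (1:1:1 matching).** Each case is again considered with controls under the same rule: "and all remaining potential controls with equal or longer time at risk".
- **Outcome model.** "After 1:1 matching, the risk of CAPA was compared between Graz and the other centers by means of multivariable logistic regression". The other covariates are the EORTC/MSGERC risk factor and ECMO. There is no time axis.
- **Caveat (Secondary analyses).** The SAP says that "residual immortal time bias was present in patients from Genoa and Rennes in this secondary analysis", because matched controls "always remained alive for at least the time at risk of their respective case from Graz in the primary analysis". It gives no corresponding caveat for the CAPA analysis.
- **Unmatched comparison.** Table 2 compares CAPA rates per ICU patient-day before matching. The methods call it descriptive and unadjusted.

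**The concern.** A control's total ICU stay is known only after its window has begun, and it includes whatever CAPA did to that stay. A Rennes patient with the median stay of 14 days (Table 1) cannot be paired with a case at the median window of 15 days (Table 3). If CAPA had prolonged that stay by one day, the patient would be eligible and the CAPA would count. If CAPA had led to earlier death or discharge, patient and event would both drop out. Truncation equalizes the windows of the selected patients but leaves the selection in place. The equal time at risk of 15 (10-23) days in Table 3 is produced by truncation and says nothing about balance in actual stay.

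At stake are the matched odds ratios in Tables 5 and 6, which carry the primary conclusion. Both come from the same eligibility rule, so their agreement does not test it.

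**Working it through.** **1. The plan's own figures.** Table 2: (50/12,426)/(4/2,368) = 4.024/1.689 = 2.38, exact 95% CI 0.87-9.08, mid-P 0.0720, as printed. Crude matched odds ratios from 17, 2 and 4 events in 83 each: Rennes (17/66)/(4/79) = 5.09; Genoa (2/81)/(4/79) = 0.49. These are compatible with the adjusted 6.07 and 0.59. The adjusted values need patient data and cannot be recomputed.

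**2. Size of the selection effect on the control side.** The documents do not give the effect of CAPA on stay, so it is assumed: CAPA multiplies the remaining ICU stay by m. Inputs: lognormal stays from the Table 1 quartiles, steroid-treated pools of 169 and 187, case windows with median 15 (IQR 10-23) capped at 53, longest case first, 600 runs per setting. Bias factor = control CAPA odds at m divided by control CAPA odds at m = 1, with the Graz side held fixed. Each cell gives constant hazard / early onset.

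| Center, how the control is picked | m = 0.5 | m = 2 |
|---|---|---|
| Rennes, random among eligible | 0.66 / 0.65 | 1.30 / 1.32 |
| Rennes, nearest stay | 0.99 / 0.93 | 0.86 / 0.87 |
| Genoa, random among eligible | 0.79 / 0.73 | 1.27 / 1.20 |
| Genoa, nearest stay | 1.25 / 1.26 | 0.67 / 0.69 |

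Monte Carlo error is about 1-2% for Rennes and 3-4% for Genoa. The direction reverses with the picking rule. Dividing the stated odds ratios by the extremes of this table gives Rennes 6.07/1.32 = 4.6 to 6.07/0.65 = 9.3, and Genoa 0.59/1.27 = 0.46 to 0.59/0.67 = 0.88. For m = 0.25 to 3 the largest Rennes factor is 1.43, and the lower confidence limit becomes 1.76/1.43 = 1.23, still above 1.

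**3. Null simulation with a propensity score and a Graz window that can respond to CAPA.** The true odds ratio is 1. There were 1,500 replicates, with an assumed CAPA hazard of 0.006 per day and Graz windows of 60-100% of remaining stay. Ranges cover three assumptions on how CAPA alters the Graz window.

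| Assumption | Time at risk in score | Eligibility only |
|---|---|---|
| CAPA and stay unrelated | 0.91-0.99 | 0.91-1.00 |
| CAPA adds 10 days | 0.91-1.12 | 1.14-1.35 |
| CAPA adds 20 days | 0.73-1.07 | 1.22-1.49 |
| Half of CAPA patients die within 5 days | 0.80-1.09 | 0.61-0.84 |

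**4. Can Table 2 serve as the check?** Take its patient-days to cover the patients in Table 1.

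- Genoa: 3989/239 = 16.7 days per patient. Quartiles of 12, 21 and 42 force a mean of at least 0.25 x (0 + 12 + 21 + 42) = 18.75.
- Rennes: 8437/192 = 43.9 days, against a median of 14 (IQR 10-27). The longest-staying quarter would have to average at least 4 x 43.9 - (10 + 14 + 27) = about 125 days.
- The standardized differences in Table 1 (+0.256 against Rennes, -0.164 against Genoa) order mean stay as Rennes < Graz < Genoa. Table 2 gives the reverse: 43.9, 28.5 (2368/83) and 16.7.
- If the two totals were exchanged, the means would be 3989/192 = 20.8 and 8437/239 = 35.3, in the right order. The rates would be 38/3989 = 9.53 (Rennes) and 12/8437 = 1.42 (Genoa) per 1000. The pooled IRR uses only the sum and stays 2.38.

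**The case against.** The strongest reply is that the bias is conditional and unsigned. If CAPA and stay are unrelated there is little of it. Time at risk is a listed matching variable, and with it in the score every range above that assumes a link includes 1. The printed intervals (1.76-20.91 and 0.10-3.53) are far wider than the bias. All of this stands, and it limits the point to a missing check and a missing limitation.

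It can also be said that Table 2 is free of the rule. That is true, but Table 2 pools two centers whose matched results point in opposite directions, includes patients without steroids, adjusts for nothing, and does not agree with Table 1.

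A reader might infer more than the documents support:

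- **That the rule visibly removed CAPA cases.** Keeping 83 of 169 and 83 of 187 controls follows from any 1:1 match to 83 cases. Control CAPA falls from 50 to 19, but proportional sampling predicts 50 x 166/431 = 19.3. The proportions are 11.6% (50/431) before and 11.4% (19/166) after. This neither shows nor excludes bias.
- **That this is immortal time bias.** That label fits the survival analysis. With CAPA as outcome, controls are at risk on every day of the window; the problem is who was selected.
- **That Graz patients were CAPA-free when posaconazole began**, which would favor the drug. The documents do not state that condition.
- **That the Graz rate can be recomputed over the prophylaxis windows and set against Table 2's control rate.** That compares truncated Graz time with untruncated control time.

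A Cox model is not a clean replacement either. In the same simulation under the null it gives 0.99-1.01 when followed to ICU discharge. Censored at the end of prophylaxis, it gives 0.82-1.28 if that end depends on stay after CAPA. With a true ratio of 2.0 confined to prophylaxis days, follow-up to discharge gives 1.60-1.69. If Graz patients are more severely ill, neither method removes the center difference (0.70-0.77 matched, 0.70-0.73 Cox). It belongs beside the matched model, not in its place.

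**Conclusion.** The point holds in conditional form. Both matched analyses select controls on post-admission ICU stay, and truncation does not undo this. If CAPA changes stay, the odds ratios in Tables 5 and 6 can be biased in either direction. Under the assumptions shown, the factor is about 0.65-1.32 when CAPA halves or doubles remaining stay, and the null odds ratio spans 0.61-1.49 over the linked scenarios. Sign and size depend on how time at risk entered the score and on the effect of CAPA on stay; the SAP gives neither.

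A reader might infer that the rule produced the Rennes result or the gap between Rennes and Genoa. It does not: over the assumed range Rennes stays well above 1. The inconsistency in Table 2's center patient-days does not depend on these simulations. It follows from the printed figures if the patient-days cover the Table 1 patients. It affects the center-specific rates, and the pooled IRR is unaffected if the two totals were merely exchanged. The changes should be made, but nothing here overturns the analysis.

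**What to change.** 1. **Reconcile Table 2 with Table 1.** Check the Rennes and Genoa patient-days against source data and correct the center rates. Do this before any person-time analysis.
2. **Add one sensitivity analysis beside the matched model.** Fit a cause-specific Cox model for first CAPA in all steroid-treated patients (83 Graz, 169 Rennes, 187 Genoa). Use ICU day as the time scale, Graz entry at posaconazole start, control entry at ICU admission, and no selection or matching on later stay. Follow to ICU discharge or death, adjust for baseline covariates, use Firth or profile-likelihood intervals, and report Rennes and Genoa separately. State that follow-up includes Graz days after prophylaxis ended, that a version censored at the end of prophylaxis may be informatively censored, and that center differences remain.
3. **Add a limitation to the primary analysis**, worded as selection on post-admission ICU stay and not as immortal time. State whether time at risk was in the score or served only as an eligibility rule.

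The cost is small. ICU, posaconazole and CAPA timing are already needed for the SAP's windows. The EORTC/MSGERC factor appears only in the matched tables, so its values must be confirmed for unmatched controls, as must any other covariate used. The added model will be imprecise, with 4 Graz events, and it gives up exactly equal time at risk between a case and its controls.

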#### *1:1:1 matching (for sensitivity analysis)*

The 1:1 PS matching described above is based on minimizing the distance between a case and a control. Therefore, for a given case from Graz, the two 1:1 PS matching procedures separately selected a control from Rennes and a control from Genoa. However,

this triplet of individuals may be not the one that minimizes the area or perimeter of the triangle formed by the three subjects [4]. Therefore, as sensitivity analysis, we conducted a logistic regression on all patients with observation time greater than or equal to the longest time at risk for the cases (thus, one case and all potential controls with equal or longer time at risk) to find for each subject the probability of belonging to the center of Graz (p1), the probability of belonging to the centre of Rennes (p2) and the probability of belonging to the centre of Genoa (p3). These probabilities sum up to 1, so we considered only the first two probabilities to figure each subject in a cartesian plane with x-axis p1 and y-axis p2. Then, we calculated the perimeter of the triangle resulting from each combination of the case with two controls (one from Genoa and one from Rennes) and chose the pair of controls for which that perimeter was the smallest. Subsequently, we repeated the procedure for the case with the second longest time at risk and all remaining potential controls with equal or longer time at risk. The procedure was then repeated until all cases were matched to one control from Genoa and one control from Rennes (1:1:1 matching)

#### Assessment of impact of posaconazole prophylaxis on the risk of CAPA after matching

After 1:1 matching, the risk of CAPA was compared between Graz and the other centers by means of multivariable logistic regression. Besides center, other variables included in the multivariable logistic regression model were: (i) European Organization for Research and Treatment of Cancer/Mycoses Study Group Education and Research Consortium (EORTC/MSGERC) risk factor present at ICU admission; (ii) presence of extracorporeal membrane oxygenation (ECMO). A sensitivity analysis including the same variables was also conducted after 1:1:1 matching.

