**Table 3. Demographic and clinical characteristics of patients after 1:1 matching**

Variables*	Graz (n = 83)	Rennes (n = 83)	Genoa (n = 83)	P	SD (Graz vs. Rennes)	SD (Graz vs. Genoa)
Posaconazole prophylaxis	83 (100)	0 (0)	0 (0)	<0.001	Inf.	Inf.
Age at ICU admission in years, median (IQR)**	65 (58-71)	65 (57-72)	66 (61-71)	0.949	0.016	-0.122
Male sex**	56 (68)	55 (66)	54 (65)	0.946	0.043	0.064
EORTC/MSGERC risk factor present at ICU admission***	8 (10)	5 (6)	5 (6)	0.591	0.148	0.148
ECMO	13 (16)	3 (4)	2 (2)	0.001	0.408	0.504
Treatment with tocilizumab**	2 (2)	3 (4)	1 (1)	0.599	-0.117	0.082
Systemic steroid treatment	83 (100)	83 (100)	83 (100)	-	0	0
Time at risk in days, median (IQR)**	15 (10-23)	15 (10-23)	15 (10-23)	-	0	0

ECMO, extracorporeal membrane oxygenation; EORTC, European Organization for Research and Treatment of Cancer; ICU, intensive care unit; IQR, interquartile range; MSGERC, Mycoses Study Group Education and Research Consortium; SD, standardized difference in means or proportions divided by standard error; imbalance defined as absolute value greater than 0.20 (small effect size)

\* Expressed as n (%), unless otherwise indicated

\*\* Matching variables (for details and definition of time at risk, see methods)

\*\*\* Presence of missing values (0/83 for Graz, 1/83 for Rennes, 0/83 for Genoa)

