**Table 5. Multivariable logistic regression of factors associated with development of CAPA after 1:1 matching**

Variables	OR (95% CI)	P
EORTC/MSGERC risk factor present at ICU admission	4.35 (1.15-16.49)	0.031
ECMO	1.85 (0.34-9.99)	0.475
Center		0.007
Rennes (vs. Graz as reference)	6.07 (1.76-20.91)	0.004
Genoa (vs. Graz as reference)	0.59 (0.10-3.53)	0.566

CI, confidence interval; CAPA, coronavirus disease 2019 (COVID-19)-associated pulmonary aspergillosis; ECMO, extracorporeal membrane oxygenation; EORTC, European Organization for Research and Treatment of Cancer; ICU, intensive care unit; IQR, interquartile range; MSGERC, Mycoses Study Group Education and Research Consortium; OR, odds ratio.

Overall, 4, 17, and 2 cases of CAPA were registered in Graz, Rennes, and Genoa, respectively, after 1:1 matching. The distribution of proven, probable, and possible CAPA in the different centers was as follows: Graz (n = 0 proven, n = 3 probable, n = 1 possible); Rennes (n = 0 proven, n = 10 probable, n = 7 possible); Genoa (n = 0 proven, n = 2 probable, n = 0 possible).

[figure not shown]
**Table 6 (sensitivity analysis). Multivariable logistic regression of factors associated with development of CAPA after 1:1:1 matching**

Variables	OR (95% CI)	P
EORTC/MSGERC risk factor present at ICU admission	2.84 (0.70-11.63)	0.146
ECMO	1.48 (0.29-7.50)	0.639
Center		0.002
Rennes (vs. Graz as reference)	5.10 (1.54-16.90)	0.008
Genoa (vs. Graz as reference)	0.80 (0.17-3.80)	0.776

CI, confidence interval; CAPA, coronavirus disease 2019 (COVID-19)-associated pulmonary aspergillosis; ECMO, extracorporeal membrane oxygenation; EORTC, European Organization for Research and Treatment of Cancer; ICU, intensive care unit; IQR, interquartile range; MSGERC, Mycoses Study Group Education and Research Consortium; OR, odds ratio.

[figure not shown]
Overall, 4, 16, and 3 cases of CAPA were registered in Graz, Rennes, and Genoa, respectively, after 1:1:1 matching. The distribution of proven, probable, and possible CAPA in the different centers was as follows: Graz (n = 0 proven, n = 3 probable, n = 1 possible); Rennes (n = 0 proven, n = 9 probable, n = 7 possible); Genoa (n = 0 proven, n = 3 probable, n = 0 possible).

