**Figure 1. Flow-chart of the patient selection process**

[figure not shown]
**Figure 1 legend.** Matched cohorts after 1:1 and 1:1:1 matching were both composed of 249 patients, although some different controls could have been selected (for details, see matching methods). COVID-19, coronavirus disease 2019.

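### Tables 5 and 6 fit four slopes by ordinary maximum likelihood to 22 analysed events; a Firth fit would lower the Rennes vs Graz odds ratio by about 12% without changing any conclusion

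*SAP*

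**What the plan says.** The SAP section on the impact of posaconazole after matching gives the adjusted analysis in one sentence: "the risk of CAPA was compared between Graz and the other centers by means of multivariable logistic regression". The model contains centre, the EORTC/MSGERC risk factor at ICU admission and ECMO. With Graz as the reference centre, that makes four slopes plus an intercept. The same model is repeated after 1:1:1 matching. No estimator is named, and no penalised or exact method is mentioned for this model.

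On the data, the legend of Figure 1 states: "Matched cohorts after 1:1 and 1:1:1 matching were both composed of 249 patients". The note to Table 5 reads: "Overall, 4, 17, and 2 cases of CAPA were registered in Graz, Rennes, and Genoa, respectively, after 1:1 matching". The footnote to Table 3 records one Rennes patient with a missing EORTC/MSGERC value and none elsewhere. Table 5 gives an OR of 6.07 (1.76-20.91) for Rennes vs Graz and 0.59 (0.10-3.53) for Genoa vs Graz. Table 6 gives 5.10 (1.54-16.90) and 0.80 (0.17-3.80).

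**The concern.** Ordinary ML estimates of log odds ratios have a small-sample bias that is governed by the smallest cells. Here both centre contrasts rest on four events in Graz, and the Genoa contrast also rests on two in Genoa. The Rennes vs Graz OR is the largest adjusted estimate in the report and the one most likely to be quoted in support of prophylaxis. An average upward bias in it runs in the direction of the study hypothesis.

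The SAP is also uneven on this point. The descriptive comparison before matching, with 4 + 38 + 12 = 54 events, uses exact Poisson limits and a mid-P test. The adjusted comparison has fewer than half as many events and more parameters, but uses large-sample methods.

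**Working it through.** **1. Identify the estimator and the analysed data.** The inputs are the Table 3 margins per centre, in the order Graz/Rennes/Genoa:
- patients 83/83/83
- EORTC/MSGERC factor 8/5/5
- ECMO 13/3/2
- events 4/17/2 (note to Table 5)
- one missing EORTC/MSGERC value, in Rennes

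An ML logistic fit depends only on the centre × factor × ECMO cell sizes and on the event totals by centre, by factor and by ECMO. All configurations in the search that were compatible with the margins were fitted and compared with the 12 printed ORs and limits.

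One configuration reproduces all 12 (largest deviation 0.005; next best 0.37). It has 248 patients and 22 events (Graz 4, Rennes 16, Genoa 2), with 4 events among patients with the factor and 2 among patients on ECMO. The four coefficient P-values also agree. So the fit is ordinary ML with Wald limits, and the dropped Rennes patient was a CAPA case. Events per slope: 22/4 = 5.5.

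Table 6 reproduces in the same way on 22 events (4/15/3).

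One printed value does not reproduce. The overall centre P in Table 5 is given as 0.007, while the rebuilt fit gives 0.0007 (Wald) or 0.0001 (likelihood ratio). It should be checked against the output.

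**2. Hand check of direction and source.** For a single 2×2 table, Firth's penalty amounts to adding 0.5 to each cell. Using the analysed Rennes and Graz counts without covariates:
- ML: (16 × 79)/(4 × 66) = 4.79
- Penalised: (16.5 × 79.5)/(4.5 × 66.5) = 4.38
- Leading-order ML bias of the log OR: ½(1/4 − 1/79) − ½(1/16 − 1/66) = 0.119 − 0.024 = 0.095

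Almost all of the bias comes from the four Graz events.

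**3. Firth fit of the full model.** This maximises ℓ(β) + ½ log|I(β)| on the same data and covariates.

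| Table 5 term | ML, Wald 95% CI | Firth, Wald 95% CI | Firth, profile 95% CI |
|---|---|---|---|
| Rennes vs Graz | 6.07 (1.76-20.91) | 5.32 (1.66-17.08) | 1.80-19.47 |
| Genoa vs Graz | 0.59 (0.10-3.53) | 0.65 (0.13-3.26) | 0.11-3.22 |
| EORTC/MSGERC factor | 4.35 (1.15-16.49) | 4.34 (1.21-15.64) | not computed |
| ECMO | 1.85 (0.34-9.99) | 2.07 (0.43-9.96) | not computed |

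The Rennes OR falls by 1 − 5.32/6.07 = 12%. The log shift is ln(6.07/5.32) = 0.13, about 0.2 of the ML standard error of 0.63. In Table 6, Rennes vs Graz moves from 5.10 to 4.54 (Wald 1.46-14.08; profile 1.57-15.93), and 1 − 4.54/5.10 = 11%.

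**4. Average behaviour on this design.** Outcomes were simulated on the rebuilt Table 5 design. ML results exclude samples with no Graz event, where ML has no finite OR; this flatters ML slightly.

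| True OR | ML, back-transformed mean log OR | Log bias | RMSE, ML / Firth |
|---|---|---|---|
| 5.32 | 5.99 | ln(5.99/5.32) = 0.12 | 0.70 / 0.63 |
| 6.07 | 7.02 | ln(7.02/6.07) = 0.15 | 0.80 / 0.66 |

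Independent runs gave ML biases of 0.11 to 0.16. The RMSE of ML varied more between runs, up to 1.03. Firth's mean log bias was between −0.04 and 0.00. With true OR 5.32, the 95% Wald interval for Rennes covered 96.6% under ML and 96.0% under Firth.

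**The case against.** The strongest reply is that nothing of substance moves. The shift is about a fifth of a standard error, inside an interval whose limits differ by a factor of 20.91/1.76 = 11.9. Rennes vs Graz stays significant, and Genoa vs Graz stays null with an OR below 1. The SAP's own 1:1:1 analysis already shows readers an OR of 5.10. All of this stands, and it limits the point to a refinement. The 1:1:1 figure is no substitute for a penalised fit, though, because it is also an ML estimate and falls to 4.54.

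Two further replies also stand. Firth is not better on every measure: with a true OR of 5.32, the median estimate was 5.73 under ML and 5.07 under Firth, so on the median Firth errs low by a similar amount. And replacing a reported model once results are known is a post hoc change.

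A reader might infer several stronger claims that the documents do not support:
- *That the printed interval is unreliable.* Its coverage on this design is nominal or slightly above.
- *That the evidence weakens.* The Firth profile P for Rennes is about 0.002, against the printed 0.004. The higher lower limit (1.80 against 1.76) comes from the profile method: with Wald limits for both fits it falls from 1.76 to 1.66, and with profile limits for both from 1.95 to 1.80.
- *That ML pushes every coefficient away from 1.* Under Firth the ECMO OR moves further from 1, and the EORTC/MSGERC OR hardly changes.
- *That the fit was at risk of breaking down.* At the observed risks a centre without events was possible: (81/83)^83 = 13% for Genoa and (79/83)^83 = 1.7% for Graz. It did not occur in either matched set.

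**Conclusion.** The point holds as a modest improvement. ML on 22 events overestimates the Rennes vs Graz log OR by about 0.12 to 0.15 on average. The penalised fit of the rebuilt data lowers the reported OR from 6.07 to 5.32, with lower mean bias and lower RMSE. No conclusion changes.

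It is tempting to say that 6.07 is itself inflated by 12%. That goes too far: bias is a property of the estimator over repeated samples and cannot be shown for one data set. Nor does estimator bias account for the size of this OR, since 5.32 is still large.

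The result rests on three assumptions: the configuration rebuilt from the printed margins is the analysed data set, outcomes are independent given the covariates (as in the SAP's model), and the true OR lies near the two values simulated. Penalisation leaves untouched the larger limits of the comparison. Prophylaxis is fully confounded with centre, and the two control centres point in opposite directions (6.07 and 0.59).

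**What to change.** Fit Tables 5 and 6 by Firth penalised logistic regression with profile-likelihood intervals and the same covariates, and print the current ML fit beside it. In Table 5, Rennes vs Graz then reads 5.32 (1.80-19.47) and Genoa vs Graz about 0.65. In Table 6, Rennes vs Graz reads about 4.54. State in both tables the numbers of patients and events analysed and, once confirmed from the data, that a Rennes CAPA case is excluded for a missing covariate. Label the penalised fit as added after results were known.

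The work is a change of one procedure. The costs are a headline OR about 12% smaller, an ECMO OR that rises from 1.85 to 2.07, and slightly inflated fitted risks (23.7 fitted against 22 observed events in Table 5).

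### ECMO enters the primary model with no time window, so ECMO started after CAPA or outside the matched time at risk is not excluded, and the ECMO term rests on about two CAPA patients

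*SAP*

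**What the plan says.** In the SAP section on the impact of posaconazole after matching, the multivariable logistic model contains center and two further covariates. They are listed together: "risk factor present at ICU admission; (ii) presence of extracorporeal membrane oxygenation (ECMO". The first is tied to ICU admission. The second, "presence of extracorporeal membrane oxygenation (ECMO", carries no date, and Tables 3 and 5 add none.

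The 1:1 matching section cuts each control's follow-up to the length of the matched case's: "we considered only the period of time at risk in controls (starting from intensive care unit admission". It does not say whether covariates are read within that window, and it says nothing about the order of ECMO and CAPA. ECMO is not among the matching variables.

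Table 5 reports only the model that includes ECMO, with Rennes versus Graz at "6.07 (1.76-20.91". The 1:1:1 sensitivity analysis (Table 6) uses the same covariates.

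**The concern.** ECMO can begin at any point in an ICU stay. Without a stated window, the covariate may include ECMO started after CAPA developed, or, in a control, ECMO started after the day on which follow-up was cut. ECMO that follows CAPA may be a consequence of the outcome. Adjusting for it does not control confounding and can distort the center contrast, which is the only estimate of the posaconazole effect that the matched analysis offers.

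The timing matters more for this variable than it would for a balanced one. After 1:1 matching, ECMO is present in 13, 3 and 2 patients in Graz, Rennes and Genoa (standardized differences 0.408 and 0.504), and it is the only covariate flagged as imbalanced. The imbalance persists after 1:1:1 matching (13, 4 and 2). Since Table 6 uses the same ECMO variable, it does not test the point.

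**Working it through.** **Inputs (SAP Tables 3 and 5, 1:1 matching)**

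| | Graz | Rennes | Genoa |
|---|---|---|---|
| Patients | 83 | 83 | 83 |
| CAPA | 4 | 17 | 2 |
| EORTC/MSGERC factor | 8 | 5 | 5 |
| ECMO | 13 | 3 | 2 |
| Missing EORTC/MSGERC value | 0 | 1 | 0 |

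**Model.** logit P(CAPA) = b0 + b1·(EORTC/MSGERC) + b2·(ECMO) + b3·(Rennes) + b4·(Genoa), fitted by maximum likelihood with Wald intervals. The fit depends only on the number of patients in each covariate pattern and on the CAPA totals by center, by risk factor and by ECMO. The unknowns are therefore:

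- how many patients in each center had both the risk factor and ECMO;
- how many CAPA patients had the risk factor, and how many had ECMO;
- the CAPA and ECMO status of the one Rennes patient with a missing value.

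**Step 1: reproduce Table 5.** All combinations consistent with the margins were tried, with 1 to 12 CAPA patients having the risk factor and 1 to 9 having ECMO. Exactly one matches all 12 printed ORs and limits to two decimals:

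- 248 patients and 22 events, the dropped Rennes patient being a CAPA case without ECMO;
- 4 CAPA patients with the risk factor and 2 with ECMO;
- both factors together in 2 Graz patients and in none elsewhere.

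It gives 4.35 (1.15-16.49) for the risk factor, 1.85 (0.34-9.99) for ECMO, 6.07 (1.76-20.91) for Rennes and 0.59 (0.10-3.53) for Genoa. It also returns the four printed P values for these terms (0.031, 0.475, 0.004, 0.566).

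**Step 2: drop ECMO, same 248 patients.** Rennes versus Graz is 5.46 (1.68-17.76), P = 0.005. Genoa versus Graz is 0.53 (0.09-3.01), P = 0.47. Including ECMO therefore raises the Rennes OR by 6.07/5.46 − 1 = 11%. For reference, the crude Rennes OR is (17/66)/(4/79) = 5.09 on all patients and (16/66)/(4/79) = 4.79 on complete cases.

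**Step 3: suppose one of the two ECMO-CAPA patients started ECMO after CAPA, and recode that patient as non-ECMO.** The reconstruction does not say which center the patient belongs to, so each was tried.

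| Recoded patient | ECMO OR | Rennes vs Graz | Genoa vs Graz |
|---|---|---|---|
| Graz, no risk factor | 0.77 | 5.30 (1.60-17.57) | 0.51 |
| Graz, with risk factor | 0.86 | 5.38 (1.62-17.82) | 0.52 |
| Rennes | 0.89 | 5.37 (1.59-18.11) | 0.52 |
| Genoa | 0.75 | 5.27 (1.58-17.55) | 0.51 |

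One start date is enough to turn the ECMO OR from above 1 to below 1 and to remove the whole rise from 5.46 to 6.07.

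**Step 4: suppose instead that late ECMO occurred only in Graz patients without CAPA.** Recoding 3, 6 or 9 of them gives Rennes ORs of 6.06, 5.99 and 5.84, with lower limits of 1.75 or above.

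**Step 5: the 1:1:1 set.** The closest reconstruction of Table 6 gives 5.09 for Rennes against the printed 5.10, with the other ORs and limits matching. Without ECMO it gives 4.83 (1.50-15.59).

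**The case against.** A reader might infer that the model counts ECMO at any time in the stay. The documents do not say so: they give no timing. The sentence on control follow-up is written for the study analyses in general and can fairly be read as limiting control ECMO to the truncated window. That objection stands against any claim that covariates were left uncut. It does not settle the order of ECMO and CAPA, which that sentence does not address for cases or for controls. Tocilizumab and steroid receipt are likewise undated, but nothing shows that they were recorded over the whole stay.

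A reader might also infer from 5.46 against 6.07 that the headline OR is inflated. This does not follow. ECMO is more frequent in Graz and has an OR of 1.85, so a properly timed baseline confounder with the same counts would move the estimate by the same amount. The comparison is of adjustment with no adjustment, not of early with late ECMO. Nor is the model without ECMO a neutral benchmark, because it leaves the largest remaining imbalance unadjusted.

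The effect is also modest. The largest move found is from 6.07 to 5.27, or 13%, inside an interval whose limits differ by a factor of about 12 (20.91/1.76). The ECMO coefficient itself is a nuisance term with P = 0.475.

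**Conclusion.** The point holds as a gap in the covariate definition that allows a post-outcome variable into the primary model. The SAP dates one covariate and leaves the other undated, and nothing in it rules out ECMO begun after CAPA. The Rennes versus Graz OR is sensitive to this: about 5.3 to 5.4 if one ECMO-CAPA patient is recoded, 5.46 without ECMO, and 6.07 as printed. Bias is not shown. In every 1:1 scenario run, Rennes versus Graz remains significant and Genoa versus Graz remains non-significant, so the study's reading does not change.

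The figures rest on cell counts inferred from published margins and on a complete-case fit. Only one configuration matches Table 5, but they should be confirmed on patient data. How many of the 18 ECMO patients started late is not given. Among CAPA patients it lies between 0 and 2.

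**What to change.** Code ECMO as present only if it started before CAPA and within the matched time-at-risk window, for cases and controls alike, and state this rule in the methods and in the table footnotes. Report the center ORs with and without ECMO side by side in Tables 5 and 6. The second display also helps because ECMO that precedes CAPA may still follow the start of posaconazole, which the recoding does not remove.

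State when tocilizumab and steroid receipt were ascertained. Re-matching on re-dated versions of these is not part of this fix: controls are chosen sequentially from those remaining, so one changed match could alter later ones and require every matched table and figure to be redone.

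The cost is a lookup of ECMO start dates in existing records, one or two extra model runs per table, and possibly a slightly different headline OR.
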